5.3.1.1 Participant selection

There will be **NO EXCEPTIONS** (waivers) to eligibility requirements at the time of randomisation. Questions about eligibility criteria should be addressed PRIOR to attempting to randomise the participant.

The eligibility criteria for this trial have been carefully considered and are the standards used to ensure that only medically appropriate participants are entered. Participants not meeting the criteria should not be entered into the trial for their safety and to ensure that the trial results can be appropriately used to make future treatment decisions for other people with similar diseases or conditions. It is therefore vital that exceptions are not made to these eligibility criteria.

Participants will be considered eligible for enrolment in this trial if they fulfil all the inclusion criteria and none of the exclusion criteria as defined below.

Investigators are encouraged to contact the SIGHT Trial Team for guidance in assessing eligibility in relation to exclusion criteria prior to approaching the patient about the trial if required.

5.3.1.2 Participant Inclusion Criteria

- Aged at least 18 years at the time of consent
- Stroke confirmed with clinical brain imaging (CT and/or MRI), not neck or brain vessel imaging (CTA, MRA, DSA)
- Between 1-week and 60-days post-stroke
- Signs of neglect on at least one of the following:
 - Star Cancellation Score ≤51, or
 - BIT line bisection score ≤7, or
 - Oxford Cognitive Screen Cancellation accuracy score <42 and either Oxford Cognitive Screen Cancellation Object score >1 or < -1, or Oxford Cognitive Screen Cancellation Space score >3 or < -2
- Able to follow a one-stage command "grasp this pencil/pen with your less affected arm" as demonstrated by another
- Able to sit with or without support in front of a table for 30 continuous minutes

5.3.1.3 Participant Exclusion Criteria

- Being discharged from in-patient hospital facility to home, or to an in-patient hospital facility that is not part of the regional participating hub, within the next 7 days
- Enrolled on another interventional study targeting neglect
- Limited life expectancy due to another illness or chronic condition making the 3month follow-up difficult (e.g. widespread malignancy)

For mechanistic neuroimaging study only:

 Contraindications to taking part in MRI study as assessed by the local MRI safety questionnaire (e.g., non-MRI compatible pacemaker)

5.3.1.4 Co-enrolment Guidance

Patients enrolled in the SIGHT trial are not permitted to be co-enrolled in other neglect interventional trials. For patients co-enrolled in any other trials considered for participation in SIGHT, or for patients participating in SIGHT considered for co-enrolment in other studies, permission should be sought from the Trial Management Group.

5.3.2 Screening Procedures and Pre-randomisation Investigations

Written informed consent/consultee agreement to enter and be randomised, if appropriate, into the trial must be obtained from participants or consultee in the case of adults lacking capacity to consent, after explanation of the aims, methods, benefits and potential hazards of the trial and **BEFORE** any trial-specific procedures. The only procedures that may be performed in advance of written informed consent being obtained are those that would be performed on all patients in the same situation as a usual standard of care.

The site staff will maintain a screening and recruitment log. Screening and recruitment data will be shared with the central trial team enabling NCTU to monitor activity and recommend appropriate action in a timely manner to the Trial Management Team.

5.3.2.1 Initial screening activities

Initial screening of potentially eligible participants will include a check of patients notes to confirm:

- evidence of stroke including review of radiology reports to confirm stroke lesion is visible on clinical scan
- patient meets remaining eligibility criteria where information is available
- for sites participating in the mechanistic study only, suitability for MRI (according to local procedures)

Potentially eligible participants will be provided with participant information sheet. All patients pre-screened will be recorded in the screening log.

5.3.2.2 Consent and Eligibility Confirmation

Once initial screening is complete, the following activities will be undertaken:

- Written informed consent or consultee assent will be obtained to participate
- Star Cancellation sub-test of the BIT
- Line bisection sub-test of the BIT
- Cancellation Task of Oxford Cognitive Screen
- For sites participating in the mechanistic study only, if patient is suitable and consents for MRI, complete screening for MRI (according to local procedures)

5.3.2.3 Eligible patient progression to baseline measures

Patients providing consent and meeting the minimum definition for visual neglect (Star Cancellation Score ≤51, or BIT line bisection score ≤7, or Oxford Cognitive Screen Cancellation accuracy score <42 and either Oxford Cognitive Screen Cancellation Object score >1 or < -1, or Oxford Cognitive Screen Cancellation Space score >3 or < -2) will complete the baseline measures and have relevant data collected as listed below before randomisation can occur:

- Clinical and Demographic data
- If baseline measures are not being undertaken on the same day as eligibility confirmation screening measures, repeat these:
 - o Star Cancellation sub-test of the BIT
 - Line Bisection sub-test of the BIT
 - Cancellation Task of Oxford Cognitive Screen (CT-OCS)
- Endpoint weightings line bisection task
- Oxford Cognitive Screen (OCS)
- Catherine Bergego Scale KF-NAP (CBS KF-NAP)
- NIH Stroke Scale/Score (NIHSS) extracted from clinical records (most recent only)
- Perception-Grasping Dissociation task
- Visual field assessment sub-test of the Vision Impairment Screening Assessment (VISA) tool
- Gesture Recognition sub-test of the Birmingham Cognitive Screen (BCoS)
- **Optional:** Computerised Extrapersonal Neglect Test (CENT)
- Pseudonymised clinical brain imaging scans (CT and/or MRI) uploaded to UEA via Image Exchange Portal
- Pseudonymised clinical brain imaging scan (CT and/or MRI) reports uploaded to database
- Confirmation yes/no of lesion in the Intraparietal Sulcus (IPS)
- MRI eligible patients at sites participating in mechanistic study will have the following MRI neuroimaging sequences before baseline measures are obtained:
 - o Localisation/setup scans
 - T1-weighted whole brain scan
 - o T2 FLAIR
 - o Diffusion weighted imaging scan (DTI)
 - o Resting-state functional MRI (rsfMRI)

5.4 Interventions

There are two trial arms:

Arm A – Standard care, treatment as usual (TAU)

Arm B – SIGHT Intervention + TAU

5.4.1 Arm A – Standard care, treatment as usual

Participants allocated to Arm A will only receive TAU according to NICE guidelines [42] as provided routinely in their clinical centre. TAU will be recorded for each patient and at site level.

5.4.2 Arm B – SIGHT Intervention + treatment as usual (TAU)

Participants allocated to Arm B will receive SIGHT for 7 days (30min/day) in addition to TAU over a 10-day period.

The staff delivering SIGHT will set-up the intervention in a separate room to reduce contamination (e.g., patients in Arm A being unblinded). The daily location of therapy delivery will be recorded in the CRF.

The SIGHT therapy involves repeated grasping and moving rods using the less affected arm. Three black lightweight wooden rods are used in different repetitions according to a pre-specified checklist. The therapist simply informs the participant about instructions following a pre-specified checklist and records the number of repetitions completed in each repetition and session.

5.4.2.1 Dose Interruptions and Discontinuations

In cases where participants are unable to complete the 7 sessions within the 10-day window (e.g., due to illness), the intervention team can administer additional therapy sessions to replace the missed sessions. Efficacy measures will still be undertaken between day 11 and day 16 even if intervention delivery is delayed. Therapists delivering intervention will not communicate delays in intervention delivery to blinded assessors undertaking the outcome measures at T1 and T2.

Consistent with intention to treat analysis, patients who decline to continue the intervention (i.e. discontinuations) but who agree to completion of follow-up measures will remain in the trial.

5.4.3 Accountability

Database checks will be built in to notify NCTU operations and relevant site staff of participants allocated to the intervention arm and when follow up assessments are due.

5.4.4 Compliance and Adherence

Therapists will be trained to deliver the intervention therapy during face-to-face training sessions. Additional online support for therapists will be provided during additional face-to-face training where requested and considered necessary by the intervention team. There will also be regular check-in meetings with SIGHT trained therapists and blinded assessors, separately, to monitor progress and address queries. Most therapy staff are rotational so it is highly likely that the staff who are originally trained will rotate during the duration of the study. As noted above we will use a train the trainer approach and lead site therapist will train any new staff joining the study to deliver the SIGHT intervention and randomly check this is done according to protocol.

Intervention **ADHERENCE** and **FIDELITY** will be monitored closely by the staff delivering the therapy using our existing checklists [16] during the first and last therapy sessions [17;56]. This data will be uploaded to the REDCap database at the University of East Anglia (UEA) and used to measure fidelity with SIGHT instructions and set-up. This will also capture the patient's level of engagement and fatigue.

5.4.5 Concomitant Care

All participants will receive treatment as usual for their care regardless of randomisation into this trial.

5.4.6 Protocol Treatment Discontinuation

In consenting to the trial, participants are consenting to trial treatments, trial follow-up and data collection. However, an individual participant may stop treatment early or be stopped early for any of the following reasons:

- A new diagnosis of a pathology or adverse event that impacts the participant's ability to take part in the trial or confounds response to SIGHT, e.g., cancer, upper limb fracture.
- Any change in the participant's condition that in the clinician's opinion justifies the discontinuation of treatment.
- Withdrawal of consent for treatment by the participant.
- Participant moves out of catchment area of clinical centre (acute or community).
- Death

As participation in the trial is entirely voluntary, the participant may choose to discontinue trial treatment at any time without penalty or loss of benefits to which they would otherwise be entitled. Although not obliged to give a reason for discontinuing their trial treatment, a reasonable effort should be made to establish this reason, whilst remaining fully respectful of the participant's rights.

Data collected up to the date of withdrawal will be retained and included in data analysis.

5.5 Outcomes

5.5.1 Primary Outcomes

The primary outcome measure is the **Star Cancellation sub-test of the Behavioural Inattention Test** [43]. This is a quick 5-min sensitive paper-and-pencil measure of neglect [46-47] that is clinically meaningful and has been sufficiently validated in the stroke population thus being suitable as a primary outcome measure of neglect reduction. This test was also used in our proof-of-concept study [16], informed the sample size calculation of the proposed RCT, as it is the most widely used test for neglect assessment in clinical practice [49] and is recommended as a primary neglect assessment by the European Academy of Neurology [50]. The test has excellent test-retest reliability [66], correlates well with the Barthel Index [64] and was found to be the best predictor of functional outcome when compared to other neglect tests as measured by the modified Barthel Index of Self-Care [48].

5.5.2 Secondary Outcomes

5.5.2.1. Efficacy measures

Following recommendations from the European Academy of Neurology [50], our three secondary outcomes will measure the impact of SIGHT on everyday life ability, using the CBS KF-NAP [30min; 51, 88-89], and on other neglect tests, including endpoint weightings line bisection task [5min; 78-79] and egocentric and allocentric neglect measured with the OCS Cancellation task [3min; 45]. Moreover, at 12 weeks follow-up, we will also collect the SIS [20min;83] to capture therapy effects on functional independence and mood to inform a phase III effectiveness trial.

• The endpoint weightings line bisection (LB) task [78-79] is a quick (5min) paperand-pencil measure involving participants marking the middle of lines presented centrally (aligned with patients' midline) or shifted to the left or right of the patient's midline. A bias to the side of the brain lesion is interpreted as a symptom of neglect. In our proof-of-concept study of SIGHT, LB was sensitive to therapy effects [16]. LB will be administered at baseline, T1 and T2.

- The CBS KF-NAP is a scale completed by a clinician that measures neglect during everyday-life activities (30min; 51, 88-89). The clinician observes the patient perform a list of 10 self-care activities that involve movements with upper and lower limbs in various positions (e.g., dressing, eating). The CBS KF-NAP was recommended by our PPI group and Occupational Therapist co-applicant as a clinically relevant measure of neglect in everyday life and judged by our PPI group as an important outcome for this trial. The CBS KF-NAP has excellent internal consistency [68], is sensitive to neglect [65], has excellent inter-rater reliability [67] and shows excellent correlation with Barthel index [51]. CBS KF-NAP will be administered at baseline, T1 and T2.
- The OCS Cancellation task is a quick (3min) paper-and-pencil sub-test of the OCS sensitive to neglect and with good test-retest reliability [45] and, in contrast to the other measures included, can distinguish between egocentric (space-centred) and allocentric (object-centred) sub-types of neglect. This measure will be administered at baseline, T1 and T2. There are two parallel versions of this test, and these will be alternated to reduce learning effects.
- The SIS (20min; at T2 only) is a stroke-specific patient reported outcome measure which assesses multidimensional stroke outcomes [83]. We have previously administered this scale to stroke survivors with neglect in our proof-of-concept and feasibility studies [16,17]. The SIS has been shown to have excellent internal consistency, excellent concurrent validity with SIS scores significantly correlating with the Barthel Index, the Functional Independence Measure and Fugl-Meyer Assessment [83]. The SIS includes a domain on emotion (9 items) which specifically enquires about feelings, mood, and ability to control emotions. Importantly, the emotion domain of the SIS shows excellent correlations with the Geriatric Depression Scale and the SD-36 Mental Health [83]. To reduce patient burden, we propose collecting the SIS at T2 only, and as in our c-SIGHT trial, via post [16]. Mail administration of the SIS has been shown to be feasible with missing items low [84]. As in our c-SIGHT trial, the blinded assessor will check its completion during the T2 visit and administer the scale or any missing items if incomplete.

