5.6.1.2 Baseline (T0)

Once the participant or consultee has given informed consent/assent and eligibility has been confirmed (signs of neglect on at least one of the following: Star Cancellation ≤51; or BIT Line bisection score ≤7; or Oxford Cognitive Screen cancellation accuracy <42 as well as either Oxford Cognitive Screen Cancellation Object score >1 or < -1, or Oxford Cognitive Screen Cancellation Space score >3 or < -2), local site staff will collect the baseline measures consisting of: demographic and clinical data; Star Cancellation sub-test of the BIT; Line Bisection sub-test of the BIT; cancellation task of the OCS; endpoint weightings line bisection; the Catherine Bergego Scale KF-NAP (CBS KF-NAP); NIHSS; Perception-Grasping dissociation task; visual field assessment sub-test of the VISA tool; the Oxford Cognitive Screen (OCS), Gesture Recognition sub-test of Birmingham Cognitive Screen (BCoS) and the **optional** Computerised Extrapersonal neglect test (CENT). To account for patient fatigue, these measures can be grouped together and done at different times or on different days to allow for a rest period.

5.6.1.3 Randomisation – Day 0

The completion and submission of the baseline measures will enable the database randomisation notifying the trial team and local SIGHT intervention delivery staff of the patient's trial arm. Randomisation stratification will use trial site, age of patient, neglect severity (according to the Star Cancellation) and whether a lesion is present or not on the Intraparietal Sulcus (IPS).

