5.10.4 Statistical Methods

5.10.4.1 Outcomes

Analysis will be conducted according to random group allocation (intention-to-treat principle). Baseline characteristics of the participants will be summarised using descriptive statistics by groups, n (%) for binary and categorical variables and mean (SD)/median (QIR) for continuous variables. Flow of the participants through the trial will be reported using the CONSORT flow diagram. A descriptive summary of the treatment received as well as adherence and fidelity measures will be given. A full statistical analysis plan will be pre-registered prior to completion of data collection, thus adhering to open and replicable research practices.

The clinical efficacy analysis will compare continuous outcome variables between treatment groups, using a general linear model at each time-point separately adjusting for stratification factors. To account for potential TAU variability across sites, clinical centre will be used as a co-variate. The effect of treatment will be summarised using the adjusted mean difference and 95% confidence interval. Dependent variables will include: Star Cancellation score (primary), CBS KF-NAP score, line bisection error and OCS Hearts overall, ego- and all centric scores and SIS scores in each domain.

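### The Stroke Impact Scale models could also adjust for continuous baseline Star Cancellation and CBS KF-NAP: a nearly free precision gain, of a size the protocol does not let us fix

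*Protocol*

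**What the plan says.** Section 5.5.2.1 makes the SIS a 12-week outcome without a baseline, and gives the reason: "To reduce patient burden, we propose collecting the SIS at T2 only". Its purpose is "to capture therapy effects on functional independence and mood to inform a phase III effectiveness trial".

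Section 5.10.4.1 states one model for the continuous efficacy outcomes, "using a general linear model at each time-point separately adjusting for stratification factors", and adds that "clinical centre will be used as a co-variate". The dependent variables include "ego- and all centric scores and SIS scores in each domain".

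The stratification factors are in section 5.6.1.3: "Randomisation stratification will use trial site, age of patient, neglect severity (according to the Star Cancellation) and whether a lesion is present or not". Section 5.9.1.1 shows that age, severity and IPS status each enter in two levels, with Star Cancellation banded as 0-25 or 26-51.

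Sections 5.3.2.3 and 5.6.1.2 list Star Cancellation and CBS KF-NAP among the measures taken from every participant before randomisation. Section 5.5.1 reports that Star Cancellation correlates well with the Barthel Index and predicted functional outcome better than the other neglect tests compared. Section 5.5.2.1 says that CBS KF-NAP "shows excellent correlation with Barthel index", and reports "SIS scores significantly correlating with the Barthel Index".

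**The concern.** For Star Cancellation, CBS KF-NAP, line bisection and OCS cancellation, a baseline value exists and could be added to the model. For the SIS it cannot. The stated SIS model therefore describes the patient's starting state only through a two-level age group, a two-level Star band, IPS lesion yes/no and centre. Differences in starting severity within those categories stay in the error term.

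The protocol collects two continuous baseline scores that it ties to function, and the SIS model uses neither in that form. At stake is the width of the confidence intervals for the SIS domains, which are meant to inform a phase III trial. Validity is not at stake: randomisation protects the estimate with or without these covariates.

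**Working it through.** **1. The plan's own sample size.** Inputs from section 5.7: effect size 0.51, 90% power, 5% level (taken as two-sided), two-sample t-test, 20% dropout. The t-test needs 81.8, so 82 per arm. Then 82 / 0.8 = 102.5, so 103 per arm and 206 in total. The stated figure is reproduced. It concerns the primary outcome; no effect size or power is stated for the SIS.

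**2. Patients analysed for the SIS.** Section 5.7 bases its 20% on dropout at a 12-week follow-up in feasibility trials, so it suits a T2 outcome: 103 x 0.8 = 82.4, taken as 82 per arm (164 in total).

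**3. Precision without the added covariates.** In units of the residual SD under the planned model, SE = sqrt(2/82) = 0.156, and the 95% CI half-width is 1.96 x 0.156 = 0.306 SD.

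**4. Precision with them.** Let r be the (multiple) partial correlation of the added baseline scores with a 12-week SIS domain score, given the strata and centre. The SE is multiplied by sqrt(1 - r²), and the gain is equivalent to multiplying the sample by 1/(1 - r²). The protocol gives no value of r, so a range is assumed:

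| r | sqrt(1 - r²) | SE falls by | 95% CI half-width (SD) | Equivalent extra patients |
|---|---|---|---|---|
| 0.1 | 0.995 | 0.5% | 0.305 | 1% |
| 0.2 | 0.980 | 2% | 0.300 | 4% |
| 0.3 | 0.954 | 5% | 0.292 | 10% |
| 0.4 | 0.917 | 8% | 0.281 | 19% |
| 0.5 | 0.866 | 13% | 0.265 | 33% |
| 0.6 | 0.800 | 20% | 0.245 | 56% |

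**5. Price of the two extra terms.** Two degrees of freedom among 164 patients cost roughly 2/164 = 1.2% in variance, or sqrt(1.012) = 1.006, about 0.6% in SE. At r = 0.1 this cancels the gain (0.995 x 1.006 = 1.001). From r = 0.2 upwards the gain exceeds the cost.

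**6. How far the shared Barthel link goes.** Two scores that each correlate with a third need not correlate with each other. If both correlations with the Barthel Index were 0.7 (illustrative), the CBS-SIS correlation could lie anywhere in 0.7 x 0.7 ± (1 - 0.7²) = 0.49 ± 0.51, from about 0 to 1. The statement in section 5.5.1 that Star Cancellation predicted functional outcome is the more direct support. It favours continuous Star at least as much as CBS KF-NAP.

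**The case against.** The strongest reply is that nothing here is wrong. Adjusting for the stratification factors and centre is valid, collecting the SIS at T2 only is a reasoned decision about burden, and further covariates for a secondary outcome could be left to the statistical analysis plan that section 5.10.4 announces. Section 4.1.1 also leaves some further adjustment open. Most of this stands as a limit on importance. But section 5.10.4.1 is not silent: it states a covariate set and applies it to the SIS, and improving a stated model is fair comment. The possible adjustment in section 4.1.1 concerns rehabilitation received between baseline and the first outcome assessment, not starting state. If the analysis plan already adds these covariates, the point is met.

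A second reply is that the Star band is already in the model, so the test the protocol rates highest for function is partly used. This is true and reduces any gain. The band is coarse, though. It also stops at 51 on a test with maximum 54, while patients can enter on line bisection or OCS criteria alone, so a score of 52-54 belongs to no stated band.

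A third reply is that CBS KF-NAP measures neglect in daily activities, not general disability or mood, and that NIHSS is another T0 candidate. Both are fair. The choice of covariates is a judgement, and gains will differ by domain.

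A reader might infer more than the protocol supports:

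- That the SIS is singled out as the only outcome modelled without a starting score. It is not: section 5.10.4.1 names no continuous baseline score for any outcome. The SIS differs only in that its own baseline cannot be added.
- That the missing SIS baseline is an error or biases the result. Neither follows.
- That a material loss of precision is established. Without a correlation between either baseline score and the 12-week SIS, a gain near zero cannot be excluded.

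**Conclusion.** The point holds as a minor, optional improvement in efficiency on a secondary outcome. The stated SIS model leaves out two continuous baseline scores that are already collected and that the protocol itself links to function. There is no bias, and the primary analysis and the sample size of 206 are untouched.

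The size of the gain is open. It runs from nothing useful at r = 0.1, through a 5% smaller standard error at r = 0.3, to 20% at r = 0.6. These figures assume 82 analysed per arm and partial correlations that the protocol does not supply. The gain may be negligible for the emotion domain.

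**What to change.** In section 5.10.4.1, state that each SIS domain model also includes continuous baseline Star Cancellation and continuous baseline CBS KF-NAP, fixed in advance and the same for all domains. Add that a missing baseline covariate is filled by simple imputation, so that the exclusion of missing data in section 5.10.4.5 does not remove a patient with an observed SIS. Such gaps should be rare, because section 5.6.1.3 makes randomisation depend on submission of the baseline measures. Leave SIS collection at T2 only.

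The cost is a short addition to the analysis text and two degrees of freedom per model, with no added assessment, visit or patient burden.
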